#### 4.6.2. Adverse Events

An adverse event (AE) is considered treatment emergent if the AE onset date/time is on or after study intervention start date/time. If time is missing, only date will be compared. All AE and SAE summaries (including AESI) will be based on Treatment emergent adverse events unless otherwise specified.

Adverse events will be coded using the standard Medical Dictionary for Regulatory Affairs (MedDRA dictionary).

An overview summary of AEs, including counts and percentages of participants will be produced with:

- Any AE
- AE by maximum grade
- Study intervention related AEs
- AEs leading to withdrawal from study
- AEs leading to permanent discontinuation of study intervention
- AEs leading to permanent discontinuation of study intervention or withdrawal from study
- Study intervention related AEs leading to permanent discontinuation of study intervention
- SAEs
- Non-serious AEs
- Study intervention related SAE
- Fatal SAEs
- SAEs leading to permanent discontinuation of study intervention
- AEs of special interest (3 types of AESI will be provided separately)

In addition to overall summary, separate summaries of AE will be produced according to the below table. Note that missing grade of AE will be imputed as "Severe".

	Summary by PT	Summary by PT and SOC	Summary by PT, SOC and Maximum Grade
Any AEs		Y	Y
Study intervention related AEs		Y	Y
AEs leading to permanent discontinuation of study intervention		Y	Y
Common ( $\geq 1\%$ ) AEs	Y		
Serious AEs		Y	Y
Non-serious study intervention related AEs	Y		
Serious Fatal and Non-Fatal study intervention related AEs	Y		

Furthermore, the following summaries will be produced for disclosure purpose.

- Summary of Common ( $\geq 5\%$ ) non-serious Adverse Events by SOC and PT (Number of Subjects and Occurrences)
- Summary of SAEs by SOC and PT (Number of Subjects and Occurrences)

A study intervention-related AE is defined as an AE for which the investigator classifies the possible relationship to study intervention as “Yes”. A worst-case scenario approach will be taken to handle missing relatedness data, i.e., the summary table will include events with the relationship to study intervention as ‘Yes’ or missing.

A study intervention-related SAE is defined as an SAE for which the investigator classifies the relationship to study intervention as “Yes”. A worst-case scenario approach will be taken to handle missing data, i.e., the summary table will include events with the relationship to study intervention as ‘Yes’ or missing.

Common ( $\geq X\%$ ) AEs are defined as AEs with  $\geq X\%$  incidence (before rounding) in any treatment group.

The following listings will be produced.

- All Adverse Events
- Serious Adverse Events and Reasons for Considering as a Serious Adverse Event.
- Subject Profile for Death

#### 4.6.2.1. Adverse Events of Special Interest

The following will be considered adverse events of special interest (AESI) for the purpose of analyses: Clostridium difficile, Cardiovascular, Gastrointestinal, and Potential Acetylcholinesterase-Inhibition AESIs. The definitions and derivations are provided for each AESI in Section [6.2.2.1](#).

### **Clostridium difficile AESIs**

This will be included in the overall summary of AEs.

### **Cardiovascular and Gastrointestinal AESIs**

The number and percentage of participants with an event will be summarized by PT, SOC and maximum grade. In addition, the incidence of AEs of GI effects and time to the first occurrence will be summarized.

### **Potential Acetylcholinesterase-Inhibition AESIs**

Any reported AE listed in the Section 6.2.2.1 with a start time no later than 12 hours after the latest dose administered, as evaluated by the investigator as per the DMID grading criteria provided in the protocol Section 10.12 Appendix 12: Division of Microbiology and Infectious Disease Adult Toxicity Tables for Adverse Event Assessment, will be included in the programmatic identification of a potential Acetylcholinesterase-Inhibition (AchE-I) AESI.

Cumulative grade score of potential AchE-I events will be calculated as the sum of the grade of each reported AE. This enables the number of AEs and the severity of each AE to be taken into account. The grading scale is defined in [Table 2](#).

**Table 2      AchE-I Cumulative Grade Score Scale**

Cumulative Grade:	0	1	2	3	4
Cumulative Grade Score:	0	1 to 3	4 to 6	7 to 10	≥11

For instance, if a participant reports two AEs, one of Grade 1 and the other of Grade 3, their cumulative grade score of 4 would result in cumulative grade 2. If a participant reports no AEs, their cumulative grade score of 0 would result in cumulative grade 0. This will be calculated for All AchE-I events, non-GI AchE-I events and GI aChE-T events, however only All AchE-I events and non-GI AchE-I events will be summarized.

AchE-I AESIs and non-GI AchE-I events will be summarized by SOC, PT and maximum grade. Separate tables will summarize AchE-I AESI by number of events and unique PT. In addition, the following parameters of AchE-I events will also be summarized, and repeated for non-GI AchE-I and GI AchE-I events.

### **Time of onset (hours):**

#### **1. Definition**

Time of onset (hours) is defined as time from first dose to the start date of the first event in hours. The first event is defined as the treatment emergent AE of which start date is the earliest within each participant. If the start time of the first event is missing, 00:00 will be imputed to calculate the time of onset. Time of onset will be rounded to the nearest hour, which will be zero hour if time of onset is <30 minutes.

## 2. Analytical approach

Time of onset will be summarised for each type of AChE-I by treatment group.

### Time since end of treatment (hours):

#### 1. **Definition**

Time since end of treatment is defined as the time from the end date of the treatment to the non-missing end date of the last event, which will be derived as follows.

- 1) For missing end date of the treatment emergent AEs, the earliest date of death and the last contact date will be imputed.
- 2) The last event will be identified as the treatment emergent AEs of the latest end date including the imputed end date per each participant. If there are more than one AEs that have the same end date but some AEs have missing end time and the other has non-missing end time, the AE with non-missing end time will be chosen as the last event.
- 3) For missing end time of the last event, 23:59 will be imputed.
- 4) Time since end of treatment will be computed as (End date/time of the last event – treatment end date/time)

#### 2. **Analytical approach**

For participants with the positive value of time since end of treatment which was calculated from non-missing end date, the time since end of treatment will be summarised for each category of AChE-I event (if any) by treatment group.

In addition, the following numbers will be presented for each AChE-I categories by treatment group.

- 1) The number of participants with the last AChE-I event end date imputed
- 2) The number of participants who have no event of any type of AChE-I with an end date after the end of treatment

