### Duration (days):

#### 1. **Definition**

Duration in days will be computed as the difference from the start date of the first event to the end date of the last event (imputed end date of last event – start date of first event + 1). The first and last events defined are the same also for the time of onset and time since end of treatment, respectively.

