#### 2. **Analytical approach**

Duration will be summarised for each AChE-I categories by treatment group.

AchE-I events with a start time less than or equal to 6 hours after the latest dose administered will also be flagged in the dataset.

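### The AChE-I time-since-end-of-treatment summary omits participants whose last event has an imputed end date, which biases it downward among those whose effects outlast dosing (minor)

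*SAP*

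**What the plan says.** SAP section 4.6.2.1 defines time since end of treatment as "the time from the end date of the treatment to the non-missing end date of the last event". Where an end date is absent, the derivation fills it in: "For missing end date of the treatment emergent AEs, the earliest date of death and the last contact date will be imputed". That filled-in date can decide which event counts as the last one: "The last event will be identified as the treatment emergent AEs of the latest end date including the imputed end date per each participant".

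The analytical approach then limits who is summarised: "For participants with the positive value of time since end of treatment which was calculated from non-missing end date". Two counts accompany the statistics, for each AChE-I category and treatment group: "The number of participants with the last AChE-I event end date imputed" and "The number of participants who have no event of any type of AChE-I with an end date after the end of treatment".

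The next item, Duration, handles the same open events differently. It runs from the start of the first event to the "imputed end date of last event", and no participant is excluded: "Duration will be summarised for each AChE-I categories by treatment group".

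**The concern.** Time since end of treatment is the only planned statistic that measures directly how long AChE-I effects last once dosing has stopped. Protocol section 8.3.7 names these events as being of special interest. A participant whose event is ongoing at last contact has a known minimum persistence. That is a right-censored observation, not an absent one. Leaving her out makes entry to the summary depend on the quantity summarised, and the values lost tend to be long.

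The rule can also discard a fully observed time. If a participant has one event that resolved after treatment and another that is still open, the open one becomes her last event and she leaves the summary altogether.

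At stake is the description of reversibility in one safety table. The unresolved share may also differ between arms, which would make the two columns less comparable.

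**Working it through.** **Inputs.** The derivation steps are in SAP 4.6.2.1. The default statistics, including both mean and median, are in SAP 4.1.1. The five-day twice-daily course is in protocol section 6.1 and the Follow-up Visit on Day 28 ± 3 in section 1.3. The documents do not give the share unresolved (u), the share whose events all ended by end of treatment (g) or a typical persistence. These are assumed below. The plan states no figure on this point, so there is none to reproduce.

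**Step 1: who enters.**
- Last event has a recorded end date after treatment: included.
- All events ended by end of treatment: not positive, so excluded, and covered by the second count.
- Last event has no end date: imputed, so excluded, and covered by the first count.
- One event resolved after treatment and another open: the imputed date is the later, so she is excluded and her resolved time is lost too.

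**Step 2: effect on the median, among those with persistence after treatment.** Suppose a share u is unresolved and their true times all exceed the resolved-only median. That median is then the 50(1 − u)th percentile of the whole group. If persistence is exponential, its ratio to the true median is ln[1/(1 − 0.5(1 − u))] / ln 2.

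| u | percentile reported as the median | ratio to true median |
|---|---|---|
| 2% | 49th | 0.97 |
| 5% | 47.5th | 0.93 |
| 10% | 45th | 0.86 |
| 20% | 40th | 0.74 |
| 30% | 35th | 0.62 |

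**Step 3: effect on the mean.** With a last dose on Day 6 and Follow-up on Day 25, an event still open has lasted (25 − 6) × 24 = 456 h. Assume a resolved-case mean of 48 h and 456 h for each open case. The mean with open cases included is (1 − u) × 48 + u × 456:
- u = 5%: 45.6 + 22.8 = 68.4 h, so 48 h is low by 1 − 48/68.4 = 30%.
- u = 10%: 43.2 + 45.6 = 88.8 h, low by 46%.
- u = 20%: 38.4 + 91.2 = 129.6 h, low by 63%.

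These percentages are illustrations, not bounds. After early withdrawal or death the open time may be far shorter than 456 h, and both u and the 48 h are assumed.

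**Step 4: the restriction to positive values.** This works the other way if the reference group is everyone with an AChE-I event. Set participants whose events ended by end of treatment to zero. The median over everyone, in units of the exponential mean, is ln[1/(1 − (0.5 − g)/(1 − g))]. For g = 20% it is ln(1/0.625) = 0.470, and for g = 40% it is ln(1.2) = 0.182. The reported median with u = 10% is ln(1/0.55) = 0.598 in both cases, which is higher. The downward bias is therefore specific to participants whose effects outlast dosing.

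**Step 5: Duration set beside it.** Duration takes open events at the imputed date, so their known minimum length does enter a statistic. But it starts at first onset, so it mixes time on treatment with time after it, and it counts the censoring date as an observed end. SAP 6.2.9 also says that imputed partial dates are not used for durations. Whether a wholly absent end date counts as partial is not stated, and the two sections should be reconciled.

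**The case against.** The exclusion is disclosed. The variable is defined on recorded end dates, and both kinds of excluded participant are counted by category and arm, so an imbalance between arms would be visible. Duration includes the open events. Few may be open in any case: protocol section 8.3.3 follows events of special interest until they resolve, stabilise or are otherwise explained, or the participant is lost. Section 2.3.1 describes the enzyme inhibition seen in vitro as rapidly reversible. The summary is descriptive and carries no test or threshold.

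Most of this stands and limits the point. It does not remove it. A count shows how many values are absent but not how long they were, and Duration answers a different question. Follow-up may end with an event stabilised or the participant lost, so open events remain possible, and the SAP itself plans for them.

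A reader might go further and infer that the AChE-I outputs describe only participants who recovered, that open events enter no statistic, or that persistence is understated for everyone with an AChE-I event. The documents do not support these readings. Duration contradicts the first two and Step 4 the third. Nor does the rule remove every unresolved case and nothing else. An absent end date may be unknown rather than ongoing, and when events tie on end date the one with a recorded end time is chosen.

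**Conclusion.** The point holds in a limited form. Among participants whose AChE-I effects outlast dosing, excluding last events with an imputed end date biases the mean and median time since end of treatment downward when those events are truly ongoing and longer than typical. The amount depends on the unresolved share, which is unknown. On the exponential assumption the median is low by about 7%, 14% and 26% at 5%, 10% and 20% unresolved. The mean is more sensitive, but any percentage for it rests on assumed inputs. The planned counts and Duration make the omission visible without correcting the statistic. This is a minor matter of descriptive safety reporting. It touches neither the primary analysis nor any decision rule.

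**What to change.** In SAP 4.6.2.1, define the group as participants with an AChE-I event that ended after, or was ongoing after, the end of treatment. Summarise time since end of treatment by Kaplan-Meier, giving the median and quartiles by treatment group for all, GI and non-GI AChE-I events. Right-censor events without an end date at the death or last-contact date that the SAP already derives. Where the data show that an event resolved on an unknown date, footnote it, since last contact is then an upper limit and not a censoring time. Keep both planned counts.

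The cost is a wording change and one reprogrammed table, with no new data. The downside is that the persistence figure may look less favourable if open events exist.

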### Duration (days):

#### 1. **Definition**

Duration in days will be computed as the difference from the start date of the first event to the end date of the last event (imputed end date of last event – start date of first event + 1). The first and last events defined are the same also for the time of onset and time since end of treatment, respectively.

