## 6.2.9. Handling of Partial Dates

Element	Reporting Detail									
General	
 
Partial dates will be displayed as captured in participant listing displays.
 
However, where necessary, display macros may impute dates as temporary variables for sorting data in listings only. In addition, partial dates may be imputed for 'slotting' data to study phases or for specific analysis purposes as outlined below.
 
Imputed partial dates will not be used to derive study day, time to onset or duration (e.g., time to onset or duration of adverse events), or elapsed time variables (e.g., time since diagnosis). In addition, imputed dates are not used for deriving the last contact date in overall survival analysis dataset.
 
									
Adverse Events	
 
Partial dates for AE recorded in the CRF will be imputed using the following conventions:
 
 
 
 Missing start time (AChE-I only)	Midnight 0:00:00 will be used for AEs with missing start time to determine if it's AChE-I.	
 
		Missing start time (AChE-I only)	Midnight 0:00:00 will be used for AEs with missing start time to determine if it's AChE-I.						
Missing start time (AChE-I only)	Midnight 0:00:00 will be used for AEs with missing start time to determine if it's AChE-I.									

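### The AChE-I duration measure is a first-onset-to-last-resolution span, so it overstates time with symptoms when a participant has separated events

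*SAP*

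**What the plan says.** SAP 4.6.2.1 defines three time measures for AChE-I adverse events of special interest and summarises each by treatment group. They are produced for all AChE-I events and again for the non-gastrointestinal and gastrointestinal groups.

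- **Duration (days).** It is "the difference from the start date of the first event to the end date of the last event", with the formula "imputed end date of last event – start date of first event + 1".
- **First event** (under Time of onset). "The first event is defined as the treatment emergent AE of which start date is the earliest within each participant".
- **Last event** (under Time since end of treatment). "The last event will be identified as the treatment emergent AEs of the latest end date including the imputed end date per each participant".
- **Missing end dates** (same place). "For missing end date of the treatment emergent AEs, the earliest date of death and the last contact date will be imputed".
- **What qualifies.** A term on the list in SAP 6.2.2.1 "with a start time no later than 12 hours after the latest dose administered".

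For time since end of treatment, the SAP restricts the summary to values based on non-missing end dates. It also reports how many participants had the end date of their last AChE-I event imputed. The duration summary carries no such restriction. Separately, the general entry in SAP 6.2.9 says "Imputed partial dates will not be used to derive study day, time to onset or duration".

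**The concern.** A reader of a table headed Duration will take it as time with symptoms. The SAP's quantity is the distance between two dates that may belong to different events. The term list in SAP 6.2.2.1 covers nausea, diarrhoea, hyperhidrosis, dyspnoea, asthma and many others, so a short gastrointestinal event early in treatment and a short event of another kind later can be joined into one figure. Qualifying onsets are tied to doses taken twice daily for five days (Protocol 6.1), so several short, separated events in one participant are a plausible pattern.

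The table therefore cannot tell brief repeated effects from one sustained effect, which is a main reason for tabulating the duration of these events. Two lesser points go with it. The definitions of first and last event refer to treatment-emergent adverse events without limiting them in words to AChE-I events within the category. And an event with no end date is closed at death or last contact, then enters the duration summary alongside observed values.

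**Working it through.** The documents state no duration figure for these events, so there is nothing to reproduce. The check applies the SAP formula to constructed patterns.

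**Inputs.** Duration formula and first/last event rules: SAP 4.6.2.1. Course: twice-daily dosing for 5 days (Protocol 6.1), so with a 12-hour onset window qualifying onsets fall on about Days 1 to 5 or 6. Follow-up Visit: Day 28 ± 3 (Protocol 1.3).

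**Formulas.** Span = last end date − first start date + 1. Event days = number of distinct calendar days with an event ongoing.

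| Pattern | SAP span (days) | Event days |
|---|---|---|
| One event, Day 1 | 1 − 1 + 1 = 1 | 1 |
| One-day events, Days 1 and 2 | 2 − 1 + 1 = 2 | 2 |
| One-day events, Days 1 and 4 | 4 − 1 + 1 = 4 | 2 |
| One-day events, Days 1 and 5 | 5 − 1 + 1 = 5 | 2 |
| One-day events, Days 1 and 6 | 6 − 1 + 1 = 6 | 2 |
| One continuous event, Days 1 to 5 | 5 − 1 + 1 = 5 | 5 |

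The fourth and sixth rows get the same reported value. In the fourth the overstatement is 5/2 = 2.5-fold, and the longest single event lasts 1 day.

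**Illustration by number of events.** Assume k one-day events on distinct days of an L-day course, all placements equally likely. Mean span = (k − 1)(L + 1)/(k + 1) + 1. The span exceeds k unless the days are consecutive, so the share overstated is 1 − (L − k + 1)/C(L, k).

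| L | k | Mean span | Event days | Share overstated |
|---|---|---|---|---|
| 5 | 1 | 1.0 | 1 | 0% |
| 5 | 2 | 6/3 + 1 = 3.0 | 2 | 1 − 4/10 = 60% |
| 5 | 3 | 12/4 + 1 = 4.0 | 3 | 1 − 3/10 = 70% |
| 6 | 2 | 7/3 + 1 = 3.3 | 2 | 1 − 5/15 = 67% |
| 6 | 3 | 14/4 + 1 = 4.5 | 3 | 1 − 4/20 = 80% |

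**Imputed end dates.** An event starting on Day 1 with no end date, in a participant last seen on Day 28, is given 28 − 1 + 1 = 28 days; last seen on Day 31, it is 31 days. If the event was still ongoing, that is a minimum. If it had resolved undocumented, it is too long.

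**Other AChE-I displays.** SAP 4.6.2.1 also gives incidence by system organ class, preferred term and grade; numbers of events and of unique terms; cumulative grade; onset time; and time since end of treatment. None gives days with symptoms or the length of a single event.

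**The case against.** The case for leaving the definition alone has several sound parts.

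- **It is exact for the simplest cases.** A single event, or contiguous events, with recorded dates gets the right value. A reader might infer that brief effects will generally be reported as lasting most of the treatment course. The documents do not support that: it needs separated events or an imputed end date, and nothing says how often either occurs.
- **The events are not arbitrary.** They come from a prespecified list with a dose-related onset window, and the surrounding text applies the measures by AChE-I category. The literal definitions still need that limit written in.
- **SAP 6.2.9 is not a flat contradiction.** A reader might take it as forbidding the imputed date in the duration formula. It concerns partial dates, whereas SAP 4.6.2.1 sets a specific rule for missing end dates and writes it into the formula. What remains is a need to say which rule governs.
- **Imputation is not hidden.** The planned count of participants with an imputed last end date uses the same last event, so it also counts the durations that rest on imputation.
- **Excluding those participants could mislead.** Protocol 8.3.3 has non-serious events of special interest followed until resolved, stabilised or otherwise explained, or until loss to follow-up. A missing end date may therefore mark a persistent event, and dropping it would shorten reported duration.
- **Protocol 2.3.1 does not call this regimen's effects transient.** It links mild and transient non-gastrointestinal events to peak concentrations above those of this regimen.

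Event counts and the adverse event listing would let a careful reader reconstruct individual cases. That does not make the summary table mean what its label says.

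**Conclusion.** The point holds in a limited form. The SAP's duration is a span, and it overstates time with symptoms for any participant with two or more separated AChE-I events. In the clearest example it reports 5 days for 2 event days.

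The means and percentages above rest on assumed one-day events placed at random. They show direction and scale, not an expected result. In that model the excess is zero for one event and appears once there are several. A reader might infer a biased comparison between arms. That goes too far: the summary is descriptive, has no test or decision rule, and the documents do not give the number of events per affected participant in either arm.

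The primary analysis and sample size are untouched. This is a minor, worthwhile correction to a mislabelled safety measure.

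**What to change.** 1. In SAP 4.6.2.1, rename the current measure first onset to last resolution span.
2. Add, per participant and AChE-I category, the number of distinct calendar days with at least one AChE-I event ongoing.
3. Add duration per event, summarised by preferred term.
4. State that first and last event mean AChE-I events within the category being summarised.
5. Do not simply exclude events with an imputed end date. Present duration with and without them, or treat them as censored at last contact, beside the imputed-end count already planned.
6. State that the missing-end-date rule in SAP 4.6.2.1 governs these measures rather than the partial-date rule in SAP 6.2.9.

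The cost is SAP wording, a small amount of programming and one or two more tables. The start and end dates needed are already collected.
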